8.6 Concomitant interventions (treatments)

Any medically necessary treatment outside of the study is allowed. The only additional measure that could affect the study outcome is local antimicrobial therapy of the nose, for example, rinses with povidone iodine (Betadine), which could affect the nasal microbiome. For this reason, open surgery within the nasal cavity followed by antimicrobial therapy is an exclusion criterion. Further concomitant treatments such as nasal rinse therapy, antibiotic therapy, steroid therapy, and nasal decongestant therapy are recorded in the concomitant treatment survey on visits 0, 2 and 3. All patients undergo preoperative single-shot i.v antibiotic prophylaxis. Continuation of antibiotic prophylaxis or treatment depends on the surgical intervention.

8.7 Medical device accountability

The single-use formulation applicator (soft swab pre-saturated with photosensitizer) as well as the single-use nasal light illuminators (1'000 each) have been supplied by the manufacturer via approved carriers with itemized bills of lading, as were the light sources. Both light sources have been tested and approved by the technical experts of the University Hospital Zurich. All serial numbers have been noted. Expiration dates have been checked to ensure that all consumables will expire only after the completion of this study. A list of consumables used will be kept.

8.8 Return, analysis, or destruction of the medical device

The medical device and any remaining consumables will be returned to the manufacturer for further processing at the end of the study. The medical devices will be shipped in their original packaging. Since it has not been in contact with biological material, no specific safety measures need to be taken for packaging or shipping.

[figure not shown]
In the event of a medical device malfunctioning, the manufacturer's technical support service will be contacted. If the problem cannot be resolved on site, the device will be returned to the manufacturer for analysis. A replacement device will immediately be shipped to the study site to enable continuation of the study. The study will not be continued until all concerns for safety are eliminated.

9. CLINICAL INVESTIGATION ASSESSMENTS

9.1 Clinical investigation flow chart and table of clinical investigation procedures and assessments

The following flow chart (Figure 4) and schedule of activities (Table 1) capture the procedures to accomplish at each study visit.

Figure 4: Study flow chart

9.2 Assessments of outcomes

To determine the efficacy of nasal cavity disinfection with aPDT in eliminating microbes all participants undergo baseline nasal swab test (one swab for both nostrils as pooled swab). Five minutes after treatment (nasal cavity disinfection-aPDT or control intervention), participants will undergo further nasal swab testing (again pooled in both nostrils with the same swab). This endpoint will determine with high accuracy the ability of nasal cavity disinfection. Comparing the bacterial colonization score (0-27) of all nine analyzed microbe-groups between experimental and control group avoids misinterpretation of disinfection effects of unactuated methylene blue photosensitizer or chlorhexidine gluconate.

9.2.1 Assessment of primary outcome

Nasal swab microbiological testing

Nasal swabs will be collected according to routine clinical practice. All investigators are trained and routinely perform diagnostic nasal swabs on patients. Nasal swabs for microbiological analysis of primary outcome are taken 5 minutes after the study or control intervention (as described in 8.1.3).

Immediately after collection, the swab will be placed in the designated sample tube with a transport medium. The sample tube will be tightly sealed and placed in a labeled plastic bag. The specimens will be stored at room temperature and sent to the laboratory by the transport service of the University Hospital Zurich according to routine transport algorithms. Microbiological analysis will all be processed at Institute for medical microbiology of University Zurich.

As primary outcome measures the microbial colonization 5 minutes after study or control intervention is expressed as score over the nine microbial subgroups (score from 0-3 according CFU count) resulting in a variable from 0-27.

Statistical analysis with comparing intervention and control group 5 minutes score is executed as described under 11.4.2.

Nine microbial subgroups for analysis:

1. β -hemolytic (group A and group B) *Streptococcus*
2. *Staphylococcus aureus* (with discrimination in MSSA and MRSA)
3. Coagulase negative *Staphylococcus* species (incl. *Staphylococcus epidermidis*)
4. α -hemolytic *Streptococcus* species (oral or viridans-group *Streptococci*)
5. *Corynebacterium* species
6. *Candida* species
7. *Enterobacteriales*
8. *Actinomyces* species and miscellaneous aerotolerant bacteria
9. Anaerobic bacteria with focus on *Propionibacterium*

Ranges of microbial colonization and bacterial colonization score:

Name	CFU's	Score
"not detectable"	below detection limit	0
"sporadic"	$<10^4$	1
"moderate"	$10^4 - 10^5$	2
"plentiful"	$>10^5$	3

9.2.2 Assessment of secondary outcomes

Microbiological testing

The same score ranging from 0-27 is also used to express the colonization 3 minutes before intervention (baseline swab) and 14 (+/-1) days after study or control intervention (follow-up swab). Statistical analysis of baseline, post intervention and follow-up colonization scores allow for understanding the general effects of aPDT on nasal microbiota over a time period of 14 days. Analyzing the difference in microbial colonization scores of experimental and control groups between baseline, 5 minutes post intervention and 14 days after allows quantification of potential influence of concomitant treatment or disinfection effects of unactuated photosensitizer solution (methylene blue, chlorhexidine gluconate).

Only for the subgroup (open reduction and internal fixation of a midface fracture), an additional nasal swab test after 2 days is carried out. This additional testing allows for better understanding of the short-term effects with clinical importance in the initial wound healing. The reason for testing only the subgroup is mainly in the comparable postoperative management in terms of concomitant treatment (single shot antibiotic prophylaxis, CHX mouth rinse, decongestant nasal drops), duration of surgery and hospital stay.

To analyze for shifts within the microbiological colonization without change in total number of CFU, a descriptive subgroup analysis of the nine microbial groups is performed.

Obtaining personal data

Data on concomitant treatments will be taken from clinical information system KISIM.

Survey

The standardized survey for expected aPDT side effects will be conducted during clinical visit on the first postoperative day and regular 14 day (+/- 1d) postoperative follow-up.

9.2.3 Assessment of safety outcomes

9.2.3.1 Adverse events

Adverse events will be documented in the eCRF. The type of adverse event, its severity or intensity, time of onset and occurrence, duration, resolution, and association with the medical device will be recorded. It will be noted whether an adverse event is to be classified as expected/unexpected and serious. All immediate local treatment effects and all delayed local effects will be recorded to assess safety. At the second visit, participants will be asked about any adverse effects that occurred in the meantime (14; +/- 1 days).

9.2.4 Assessments in subjects who prematurely stop the investigation

The reason for withdrawal will be noted in the eCRF as described in chapter 7.4. In case of withdrawal, no further data will be collected. If the reason for the withdrawal is problems related to the safety or performance of the medical device, the principal investigator will ask the subject for permission to follow their status and condition outside of the investigation. The data collected at the time of withdrawal will be used for statistical analysis in accordance with Art. 3 Abs. b ClinO-MD and subsequently anonymized. All biological material will be destroyed after evaluation.

9.2.5 Follow-up of the subjects after the regular termination of the investigation

If the performed surgical procedure requires further follow-up, this is carried out in the Department for Oral- and Maxillofacial Surgery at University Hospital Zurich. The study intervention needs no additional care after participation in this study. Patients are asked to contact their healthcare provider (primary care physician) and/or local public health authority in case of any medical problem after participation in this study.

9.2.6 Patients lost to follow up

Participants are considered "lost to follow-up" if they fail to report for scheduled study visits and cannot be reached to complete all protocol-required study procedures.

The following actions will be taken if a participant fails to attend a required study visit:

- The investigator will attempt to contact the participant and reschedule the missed visit for the next day and will counsel the participant on the importance of maintaining the assigned appointment and inquires as to whether the participant wishes to and/or should continue participating in the study.
- Should the participant continue to be unreachable, they will be considered to have withdrawn from the study with a primary reason of "lost to follow-up".

9.3 Procedures at each visit

9.3.1 Screening visit (Visit 0)

The screening visit takes place as part of the regular consultation hours for Oral- and Maxillofacial Surgery. Patients will be informed about the study. Informed consent will be obtained. Inclusion and exclusion criteria will be reviewed. Demographic information, patient's medical history and survey of concomitant treatments will be obtained.

9.3.2 Visit 1

The first visit will take place during preparation for surgical intervention. Patient is already under general anesthesia. Randomization takes place according to description 6.2.1.

Nasal swab + aPDT

Nasal swab test 3 minutes before the study intervention as described under 8.1.3. Administer study or control intervention as described under 8.1.1 and 8.1.2.

Nasal swab + follow up

After treatment, a second nasal swab test (5 minutes post intervention) for analysis of primary outcome will be taken.

In case of AE / SAE and/or device deficiencies the corresponding eCRF forms are recorded.

9.3.3 Visit 2

The second visit will take place on first postoperative day. The study investigator (not the same investigator who carried out the study intervention) will record the survey of concomitant treatment, survey of expected side effects and AE / SAE. In addition, scheduling of visit 3 on day 14 (+/- 1) post intervention is carried out. For outpatient procedures, visit 2 is carried out by telephone.

9.3.4 Visit 3 (only subgroup following ORIF of midface fracture)

The third study visit is on the day of discharge from hospital (day 2) and contains an additional nasal swab test (pooled for both nostrils as described under 8.1.3).

9.3.5 Visit 4

Study Visit 4 will be held combined with the regular follow-up after surgery (wound control, removing sutures etc.). Recording of survey of concomitant treatment, expected side effects, AE/SAE will be recorded. A third nasal swab test is performed for microbiological analysis to assess secondary objective. Last step during visit 4 is documentation of study end eCRF form.

10. SAFETY

10.1 Definition and assessment of (serious) adverse events and other safety related events

Adverse Event (AE) (Art. 2 Abs 57 MDR)

Any untoward medical occurrence, unintended disease or injury, or any untoward clinical signs in subjects, users, or others, whether related to the MD or not.

Serious Adverse Event (SAE) (Art. 2 Abs 58 MDR)

Any adverse event that led to any of the following:

- (a) death,
- (b) serious deterioration in the health of the subject that resulted in any of the following:
 - (i) life-threatening illness or injury,
 - (ii) permanent impairment of a body structure or a body function,
 - (iii) hospitalization or prolongation of patient hospitalization,
 - (iv) need for medical or surgical intervention to prevent life-threatening illness or injury or permanent impairment to a body structure or a body function,
 - (v) chronic disease,
- (c) fetal distress, fetal death, or a congenital physical or mental impairment or birth defect.

Note: planned hospitalization for a pre-existing condition or a procedure required by the CIP that does not result in a serious deterioration of the subject's health is not considered an SAE.

Device deficiency (Art. 2 Abs 59 MDR)

Inadequacies of a medical device (investigational device) related to its identity, quality, durability, reliability, safety, or performance, including malfunction, user errors, and inadequate information supplied by the manufacturer.

Malfunction (ISO14155)

Failure of an investigational device to fulfill its intended purpose when used in accordance with the instructions for use or the CIP.

Device deficiency with Serious Adverse Device Effect (SADE) potential (Art. 80 Abs 1 letter c MDR; ISO14155)

Any device deficiency that might have led to a serious adverse event if appropriate action had not been taken, if the intervention had not occurred, or if circumstances had been less fortunate.

Adverse Device Effect (ADE) (ISO14155)

Adverse event that is possibly, probably, or causally related to the use of an investigational device or procedure.

Serious Adverse Device Effect (SADE) (ISO14155)

Adverse device effect (ADE) that has resulted in any of the consequences characteristic of a serious adverse event (SAE).

Unanticipated Serious Adverse Device Effect (USADE) (ISO14155)

Serious adverse device effect (SADE) which by its nature, incidence, severity, or outcome has not been identified in the current version of the risk analysis report.

Causal Relationship of SAE (MDCG 2020-10/1)

Causal relationship with the medical device or the investigational procedure should be rated by the principal investigator as follows:

- **Not related:** A relationship with the device or procedure can be excluded.
- **Possible:** A relationship with the use of the investigational device is weak but cannot be ruled out completely. Alternative causes are also possible.
- **Probable:** A relationship with the use of the investigational device seems relevant and/or the event cannot reasonably be explained by another cause.
- **Causal relationship:** The serious event is associated with the investigational device or with procedures beyond a reasonable doubt.

10.2 Adverse events categorization

The adverse events are categorized by the PI using the following algorithm:

Does the AE meet the seriousness criteria?

- No, it is not serious:
 - Is the relationship to the device or the procedure possible, probable, or causal?
 - No: unrelated AE
 - Yes: ADE
- Yes, it is serious:
 - Is the relationship to the device or the procedure possible, probable, or causal?
 - No: non-related SAE
 - Yes: SADE
- Is it anticipated (within expected type, severity, and frequency of the complications)?
 - No: unanticipated SADE (USADE)
 - Yes: anticipated SADE (ASADE)

10.3 Documentation and reporting in medical device category A clinical investigations

Device deficiencies (DD) and all adverse events (AE) including all serious adverse events (SAE), will be recorded, fully investigated, and documented in the source document and corresponding case report form (eCRF) throughout the investigation period (from patient consent to the last CIP-specific procedure).

- Documentation of AEs (including SAEs) by the PI includes diagnosis or symptoms, date of onset and end of the event, treatment, resolution, severity assessment, and causal relationship to MD and/or investigation procedure (Art. 32 ClinO-MD, ISO14155).
- Documentation of DDs by the PI includes a description of the dysfunction, date of onset, investigational device information, any action taken regarding the investigational device, and whether the DD led to an AE. The principal investigator shall review all DDs and determine and document in writing whether they could have led to an SAE (DD with SADE potential) (Art 32. ClinO-MD, ISO14155).
- The information on AEs is systematically collected by clinical safety assessment at the regular visits
- no safety follow-up is required based on the benefit-risk profile and lack of known long-term adverse effects with this medical device

Safety and protective measures

If immediate safety and protective measures must be taken during the conduct of this clinical trial, the investigator must notify the CEC of these measures and the circumstances necessitating them, within 2 days.

Annual Safety Report

(As indicated under 10.3.2)

10.3.1 Foreseeable adverse events and anticipated adverse device effects

Based on the available data, there are no known foreseeable serious adverse events and anticipated adverse device effects for the medical device investigated in this study.

10.3.2 Reporting of safety related events

Reporting to the sponsor-investigator:

All SAEs, DDs, and health hazards requiring action will be reported to the sponsor-investigator by the investigators within 24 hours of becoming aware of the events. DDs will be assessed regarding their potential to lead to an SAE. Reporting on pregnancies is not required for this study.

Reporting to the Competent Ethics Committee:

The principal investigator will immediately report to the CEC any serious adverse event which has a causal relation with the MD or for which a causal relationship appears possible (Art. 33 ClinO-MD). To ensure rapid reporting, the sponsor-investigator may initially submit an incomplete report. If measures must be taken immediately to address safety and health hazards in the conduct of the investigation, the principal investigator will report these measures and the circumstances necessitating them to the CEC within 2 days (Art. 34 ClinO-MD).

Periodic safety reporting (Art. 35 ClinO-MD):

An Annual Safety Report (ASR) will be submitted annually to the CEC by the principal investigator. The ASR includes a list of all SADEs and DDs and a report on their severity, their causal relationship to the MD and procedure, and on subject safety.

Other reports are made according to the MD vigilance provisions as per Art. 87-90 MDR and Art. 67 MedDO.

All device malfunctions will additionally be recorded in the University Hospital's materiovigilance system according to the hospital guidelines.

11. STATISTICAL METHODS

Detailed methodology for summaries and statistical analyses of the data collected in this study will be documented in a statistical analysis plan. The statistical analysis plan will be finalized before database closure and will be under version control at the Department of Biostatistics, University of Zurich.

11.1 Hypothesis

The two-sided null hypothesis to be tested is that nasal cavity photodisinfection by aPDT (intervention) as an add-on treatment to 0.2 % chlorhexidine gluconate has no effect on local microbial colonization in a perioperative setting compared to 0.2 % chlorhexidine gluconate and non-light activated methylene blue (control). The corresponding alternative hypothesis is that the two treatments differ. The research hypothesis is, that the intervention will reduce local microbial colonization compared to control (superiority of the intervention).

11.2 Determination of sample size

The sample size was calculated to show the superiority of the intervention compared to the control regarding the primary outcome with a power of 90 % at a significance level of 5 %. We calculated the sample size for a Wilcoxon-Mann-Whitney test, but did this via the sample size for a two-sample t-test and by increasing the sample size using the Asymptotic Relative Efficiency (ARE) of the Wilcoxon-Mann-Whitney test (compared to the t-test), which is never less than 0.864 (17,18). The power was estimated for a range of sample sizes $n_{i=1,\dots,61} = 50,\dots,350$ with the R package sse (19). Moreover, to assess how the calculation is affected by the mean difference, θ , we varied θ from 1.5 to 4.5. For each combination of n_i and θ , we calculated the power for a two-sample t-test.

Figure 1 shows that for showing a mean difference in the primary outcome of 3 with a standard deviation of 6, a total of 170 evaluable patients would be required for a two-sample t-test. For a Wilcoxon-Mann-Whitney test we increased the sample size, dividing 170 by 0.864, which resulted in 198 patients (rounded up to an even number). Assuming a drop-out rate of 5 %, 208 patients need to be enrolled.

[figure not shown]

Figure 1: Dependence of the sample size on the mean difference between treatments, θ , assuming a standard deviation of 6. An example is shown for $\theta=3$ and a power of 90 %. The curves are smoothed and shown for illustration only.

11.3 Statistical criteria of termination of the investigation

None.

11.4 Planned analyses

11.4.1 Datasets to be analyzed, analysis populations

The full analysis set (FAS) includes all patients randomized to the trial who underwent aPDT.

11.4.2 Primary analysis

The primary outcome, bacterial colonization 5 minutes after aPDT across the nine analyzed microbe groups, expressed as a score (range 0–27), will be compared between the randomized groups (intervention vs. control) by an exact Wilcoxon-Mann-Whitney test, as implemented in the function of `wilcox_test` from the R package `coin` (20), for an improved handling of ties (compared to other implementations of the test). We will also estimate the Mann-Whitney parameter, $\varphi = \Pr[X < Y] + 0.5\Pr[X = Y]$ (with X and Y being the ordered primary outcome in the intervention and control group), a natural effect parameter associated with this test with a corresponding 95 % confidence interval. In addition, we will apply a proportional odds logistic regression model, in order to adjust for the baseline measurement of bacterial colonization and the type of surgery used for stratifying the randomization. The primary outcome will be analyzed as ordinal outcome with type of surgery and randomized treatment (intervention vs. control) as explanatory variables. This model will estimate proportional odds ratios with 95 % confidence intervals.

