5. CLINICAL INVESTIGATION OUTCOMES

5.1 Primary outcome

To objectively determine the efficacy of nasal cavity decolonization with aPDT in eliminating or significantly decreasing pathogens, relative abundance of CFU (colony forming unit) over nine analyzed microbe groups at timepoint 5 minutes after intervention, are grouped as score ranging from 0-27. The results will be adjusted to the baseline measure 3 minutes pre-intervention. Comparing bacterial colonization scores of interventions to control group allows to measure additional disinfection effect of aPDT over chlorhexidine gluconate.

Score bacterial colonization:

Name	CFU's	Score
"not detectable"	below detection limit	0
"sporadic"	<10 ⁴	1
"moderate"	10 ⁴ – 10 ⁵	2
"plentiful"	>10 ⁵	3

Nine microbial subgroups for analysis:

1. β -hemolytic (group A and group B) *Streptococcus*
2. *Staphylococcus aureus* (with discrimination in MSSA and MRSA)
3. Coagulase negative *Staphylococcus* species (incl. *Staphylococcus epidermidis*)
4. α -hemolytic *Streptococcus* species (oral or viridans-group *Streptococci*)
5. *Corynebacterium* species
6. *Candida* species
7. *Enterobacteriales*
8. *Actinomyces* species and miscellaneous aerotolerant bacteria
9. Anaerobic bacteria with focus on *Propionibacterium*

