6.2.1 Randomization

Randomization will be performed in REDCap. Clinicians conducting the postoperative surveys will not have access to the eCRF form with the randomization result and therefore be blinded against the treatment group.

Stratified block randomization with variable block size for type of surgery (osteosynthesis removal; open reduction and internal fixation of midface fractures vs other).

Explanation for stratification:

Removal of osteosynthesis material rarely requires any of the under 8.6 mentioned concomitant treatments. In addition, the patients are generally younger and have less comorbidities. Therefore, a stratified randomization to intervention and control group is justified. The second stratification for patients undergoing open reduction and internal fixation of midface fractures is necessary to build the subgroup (target size n=50) with additional swab on day 2 (day of hospital discharge). Also, this patient collective is more consistent in duration of surgery and concomitant treatment.

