11.4.3 Secondary analyses

Analyses of secondary outcomes: The secondary outcome, bacterial colonization 14 days after aPDT (measured otherwise the same way as the primary outcome) and bacterial colonization 2 days after for the ORIF midface group will be analyzed in a similar way as the primary outcome (see Section 11.4.2). The proportional odds logistic regression model will additionally adjust for concomitant treatment with nasal rinse therapy, antibiotic therapy, steroid therapy, and nasal decongestant therapy, which are prescribed depending on the surgical intervention, and may also influence bacterial colonization after 14 days. To compare bacterial colonization 5 minutes after aPDT 2 days (only ORIF midface) and 14 days after aPDT (short- and long-term), we analyze these measurements as repeated measurements together in one model. We fit a mixed-effects proportional odds logistic regression model on bacterial colonization, with treatment (intervention vs. control) and time (14 days vs. 5 min and 2 days (only ORIF midface)) as explanatory variables. In an additional model, we will add the interaction between treatment and time, in order to test for a difference in the change over time between the treatment groups.

The colonization with individual types of bacteria (9 types) at baseline, and 5 minutes and 2 days (only ORIF midface) and 14 days after aPDT will be descriptively analyzed and summary statistics (frequency and percentage of each category) will be reported by treatment group.

Subgroup analyses: For the primary outcome, subgroup analyses will be performed for the following subgroups: bacterial colonization at baseline ($>$ median vs \geq median), type of surgery and sex. For each subgroup variable, a proportional odds logistic regression model will be fitted to the primary outcome, with treatment, the subgroup variable, and the interaction between the subgroup variable and treatment as explanatory variables. A statistically significant interaction between one of the subgroup variables and treatment would indicate a different treatment effect in the corresponding subgroups. We will also estimate group-specific treatment effects (with 95 % CI), fitting a separate model for the corresponding subgroups, which will be reported together with the interaction p-value.

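### The Wilcoxon-Mann-Whitney test that sizes the trial uses neither the baseline score nor the surgery stratum, and 11.4.2 never names it as the confirmatory analysis

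*Combined protocol and SAP*

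**What the plan says.** - **Primary test (11.4.2).** The 5-minute score "will be compared between the randomized groups (intervention vs. control) by an exact Wilcoxon-Mann-Whitney test". The Mann-Whitney parameter with a 95% confidence interval goes with it. Neither baseline nor stratum enters.
- **Adjusted model (11.4.2 and synopsis).** A proportional odds model is introduced as an addition, with the stated purpose of adjusting for baseline colonization and type of surgery. The next sentence of 11.4.2 lists only type of surgery and treatment as explanatory variables.
- **Primary outcome (5.1).** "The results will be adjusted to the baseline measure 3 minutes pre-intervention".
- **Allocation (6.2.1).** "Stratified block randomization with variable block size for type of surgery", with three types: osteosynthesis removal, open reduction and internal fixation of midface fractures, and other. The section explains that removal patients tend to be younger, with fewer comorbidities and concomitant treatments.
- **Sample size (11.1, 11.2).** "The two-sided null hypothesis to be tested" is sized "with a power of 90 % at a significance level of 5" per cent, using a "mean difference in the primary outcome of 3 with a standard deviation of 6, a total of 170 evaluable patients" for a t-test. This is then enlarged for the Wilcoxon test by an efficiency "which is never less than 0.864".
- **Later time points (11.4.3).** Day 14 and day 2 "will be analyzed in a similar way as the primary outcome".

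No sentence says which analysis is confirmatory, or what follows if the two disagree.

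**The concern.** Every patient has a baseline swab scored exactly as the outcome is (9.2.2). By the timings in 8.1.1 and 8.1.2 it comes about 3 + 0.5 + 2 + 0.5 + 2 + 5 = 13 minutes before the outcome swab. If the two scores are correlated, variation between patients that has already been measured stays in the error term of the planned test.

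Allocation is also blocked within surgery type. An analysis that ignores a prognostic blocking factor overstates the variance of the treatment comparison, so its true type I error falls below the nominal 5%.

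Both features are already in the design, yet the test that carries the sample size uses neither. Section 5.1 would also lead a reader to expect a baseline-adjusted primary result, which that test does not give. Because 11.4.3 carries the approach forward, day 14 and day 2 inherit the same loss.

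**Working it through.** **1. The plan's own figures.** Inputs from 11.1 and 11.2: two-sided 5%, power 90%, difference 3, SD 6, efficiency 0.864.
- t-test, per arm: 2 × (1.960 + 1.282)² × 6² / 3² = 84.1, so 85, or 170 in total. The noncentral t distribution gives power 0.8999 at 170.
- Wilcoxon: 170 / 0.864 = 196.8, so 198 as an even number.
- Enrolled: 198 × 1.05 = 207.9, so 208.

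The stated 170, 198 and 208 all reproduce. The planned test has the power claimed for it.

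**2. Adding the baseline score.** Adjustment multiplies the residual variance by 1 − r². The documents give no r, so a range is assumed. Effective size per arm is 99 × 0.864 = 85.5, taking the same efficiency for the adjusted test. The noncentrality is 3 / [6 √(1 − r²) √(2 / 85.5)].

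| r (assumed) | 1 − r² | Power, t approximation | Power, normal approximation | Difference detectable with 90% power |
|---|---|---|---|---|
| 0 (as planned) | 1.00 | 0.90 | 0.905 | 2.97 |
| 0.1 | 0.99 | 0.905 | 0.908 | 2.96 |
| 0.3 | 0.91 | 0.93 | 0.929 | 2.84 |
| 0.5 | 0.75 | 0.96 | 0.965 | 2.58 |
| 0.7 | 0.51 | 0.995 | 0.996 | 2.12 |

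**3. Simulation check.** Assumptions: 198 patients, scores rounded and held within 0-27, mean 12, strata of 98, 50 and 50, asymptotic tests, 2,000 to 3,000 runs per cell. With no stratum effect and a difference of 3, power of the unadjusted Wilcoxon test against a rank analysis of covariance on baseline and stratum was:
- r = 0.3: 0.922 against 0.939
- r = 0.5: 0.929 against 0.969
- r = 0.7: 0.926 against 0.997

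For a difference of 2.5 at r = 0.5 it was 0.83 against 0.91. A separate run of 1,500 at r = 0.1 gave 0.922 against 0.924, so almost nothing is gained there.

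**4. Ignoring the stratum.** Same simulation under the null. The share of variance explained by surgery type is assumed.

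| Share explained by surgery type | Unstratified Wilcoxon, type I error | Stratified or adjusted test, type I error |
|---|---|---|
| 10% | 0.036-0.049 | 0.046-0.059 |
| 20% | 0.027-0.032 | 0.046-0.057 |

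Allowing for other simulation settings, about 0.02 to 0.04 is a fair range at 20%. With no stratum effect both tests sit near 5%. At 20%, r = 0 and a difference of 3, stratification alone moves power from 0.945 to 0.969.

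**5. Day 2.** The synopsis gives about 50 per arm, while 6.2.1 gives the subgroup a target size of 50. Assuming the same effect and SD, with the formula of step 2 and the t approximation:
- 50 per arm (effective 50 × 0.864 = 43.2): power 0.63 unadjusted; 0.67, 0.76 and 0.90 at r = 0.3, 0.5 and 0.7.
- 25 per arm (effective 25 × 0.864 = 21.6): power 0.36 unadjusted; 0.39, 0.46 and 0.61.

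**The case against.** **No planned power is lost.** This stands. An unadjusted test fixed in advance, with an adjusted model beside it, is a legitimate choice, and it reaches 90% on the plan's inputs. A reader might infer that the trial is underpowered; step 1 shows that it is not.

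**The gain rests on an unknown r.** This also stands. Both arms receive chlorhexidine and methylene blue between the two swabs, so a weak correlation cannot be ruled out, and at r = 0.1 the gain is negligible. The conservatism likewise depends on a stratum effect that the documents do not quantify.

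**There is an implied ranking.** A reader might infer two rival primary results, either of which could be claimed, with an error rate above 5%. The documents do not support this. The Wilcoxon test comes first, the model is introduced as an addition, and 11.2 sizes the trial for the Wilcoxon test alone; no passage allows success on either. What remains is that the ranking is never stated.

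**Section 5.1 need not refer to the deciding p-value.** This is fair: the adjusted model, by its stated purpose, would meet 5.1. But its listed explanatory variables omit baseline, so read literally no analysis in 11.4.2 delivers the adjustment.

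**A detailed analysis plan is still to come.** Section 11 defers detail to a plan finalised before database closure. That is a natural place for the change, but it does not show that the matter is settled.

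**Conclusion.** The point holds as an improvement that needs no new data and should be made; it is not a flaw in validity. The planned test ignores a baseline score and a stratum that the design already provides, and its confirmatory status has to be inferred.

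At 198 evaluable patients, a difference of 3 and SD 6, baseline adjustment adds from about half a percentage point of power (r = 0.1) to about 9 points (r = 0.7), and nothing at r = 0. Stratifying restores the nominal type I error if surgery type is prognostic and costs almost nothing if it is not.

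These sizes rest on an assumed r, an assumed stratum effect and near-normal scores in the simulation. The day-2 gain cannot be fixed until the synopsis and 6.2.1 agree on the size of the subgroup.

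**What to change.** In 11.4.2 and the synopsis, before outcomes are seen by arm:

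1. Name one confirmatory test that adjusts for the baseline score and is stratified by the three surgery types. One option that stays within coin: regress the ranks of the 5-minute score on the ranks of the baseline score within stratum, leaving arm out, then run `independence_test(residual ~ arm | surgery_type)`.
2. At a minimum, block the planned test: `wilcox_test(score ~ arm | surgery_type)`. If that remains confirmatory, say so and reword 5.1 to match.
3. Under option 1, label the unadjusted Wilcoxon test and the Mann-Whitney parameter with its confidence interval as supportive. They remain useful because the residual test has no effect estimate of its own.
4. Keep the proportional odds model for the adjusted effect estimate and add baseline score to its listed explanatory variables. It gives a conditional odds ratio under a proportional odds assumption and does not replace the rank test.
5. Use the same approach at day 14. At day 2 adjust for baseline only, since the subgroup is a single stratum, and reconcile its size between the synopsis and 6.2.1.
6. Align 5.1 with 11.4.2. Section 11.2 can stand as a conservative calculation.

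The cost is protocol and analysis-plan wording and a few lines of code, with no new data and no extra patients. Section 2.9 lists changes to the form of statistical analysis among those needing ethics committee approval, so the wording may have to go through that route.
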